## 6.2. Populations for Analysis

Safety analyses will be conducted on all patients who have received at least one dose of LY2835219.

Pharmacokinetic analyses will be conducted on patients who have received at least one dose of the LY2835219 and have sufficient samples collected to allow the estimation of LY2835219 PK parameters.

Pharmacodynamic analyses will be conducted on patients who have undergone PD assessments.

Pharmacokinetic/Pharmacodynamic analyses will be conducted on the population of the PK analyses.

Efficacy analyses will be conducted on patients who have received at least one dose of LY2835219.

## 6.3. Statistical Methods

### 6.3.1. General Considerations

Statistical analysis of this study will be the responsibility of Lilly.

CCI

Additional exploratory analyses may be conducted by Lilly as documented in a post-hoc section of this SAP.

The interpretation of the study results will be the responsibility of the investigator with the Lilly Clinical Research Physician (CRP), pharmacokineticist, statistician and clinical development associate. The Lilly CRP and statistician will also be responsible for the appropriate conduct of an internal review process for both the final study report and any study-related material to be authorized for publication by Lilly.

Approximately 200 patients will be enrolled in this multicenter open-label Phase 1 study with dose escalation CCI followed by dose confirmation in 6 tumor types. During dose escalation (Part A), patients will be enrolled into sequential cohorts; the total number of patients in a specific cohort will be determined based on the occurrence of DLTs (2-6 patients per cohort) at that dose level. In each tumor-specific expansion cohort, at least 15 and up to 45-60 patients will be treated on the twice daily schedule at a dose no greater than the MTD (200 mg every 12 hours) with administration of LY2835219 on Days 1 through 28 of a 28-day cycle, with modifications during Cycle 1 to enable PK sampling following a single dose and repeated doses.

The analyses for this study will be descriptive; no p-values will be calculated. Data analyses will be provided by cohort and for all study patients combined wherever appropriate. For continuous variables, summary statistics will include number of patients, mean, median, standard deviation, standard error, minimum, and maximum. Categorical endpoints will be

summarized using number of patients, frequency, percentages, and their standard errors. Missing data will not be imputed.

Additional exploratory analyses of the data may be conducted if deemed appropriate.

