In addition, PK/PD modeling suggested that AUC levels associated with tumor growth delay in preclinical *in vivo* efficacy studies (approximately 3600 to 9500 ng·hr/mL) should be reached in patients within a dose range of 300 to 700 mg administered once daily ([Table JPBA.4.3](#)). Based on the *steady-state exposures* observed at the Not Severely Toxic Dose in rats and the highest Minimally Toxic Dose in dogs, the median exposure multiples predicted at steady state for this clinical dose range were approximately 8 to 18 and 0.3 to 0.7, respectively.

During the dose escalation phase, preliminary analysis of PK data from the initial 4 dose levels (50, 100, 150, and 225 mg every 24 hours) indicated less than dose-proportional increases in exposure. Based on these results, a twice daily schedule was introduced in Part A with LY2835219 administered orally at the following planned dose levels: 75, 100, 150, 200, 275, 350, and 450 mg every 12 hours for 28 days. Importantly, the first planned dose level (75 mg every 12 hours) corresponded to a daily dose of 150 mg, which was 1 dose level lower than that of the highest previously explored dose level (225 mg every 24 hours). For the twice daily schedule, the highest dose of LY2835219 evaluated was 275 mg every 12 hours. At this dose level, 2 of the 3 patients experienced DLT of Grade 3 fatigue. At the next lower dose level of 200 mg every 12 hours, 1 of the 7 patients also experienced DLT of Grade 3 fatigue. Therefore, the maximum tolerated dose (MTD) was established at 200 mg every 12 hours.

During the tumor-specific expansion phases, patients initially received LY2835219 at the MTD of 200 mg every 12 hours. A preliminary interim safety review with data from 56 patients indicated that 29 patients experienced diarrhea possibly related to study drug: 17 Grade 1 (30%), 9 Grade 2 (16%), 3 Grade 3 (5%), none Grade 4 (0%), and none Grade 5 (0%). Based on the frequency of Grade 1/2 diarrhea and the observation of clinical activity at doses below the MTD, the initial starting dose was changed to 150 mg every 12 hours with JPBA amendment (f) to gain additional PK data and clinical experience around safety/tolerability. Importantly, diarrhea experienced by patients is manageable with standard anti-diarrheal agents. Therefore, early treatment with anti-diarrheal agents (e.g., loperamide) is recommended and the initial starting dose will return to the MTD of 200 mg every 12 hours with JPBA amendment (g).

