6.2.2. Dose-Escalation Phase

The dose was escalated following assessment of toxicity using the standard scoring system, Common Terminology Criteria for Adverse Events (CTCAE CCI [REDACTED] established by the National Cancer Institute (NCI). Any AEs possibly related to LY2835219 were considered as toxicities.

For the dose-escalation phase, Table JPBA.6.1 summarizes the dose levels completed for the once daily schedule (50 to 225 mg every 24 hours) and the proposed dose levels for the twice daily schedule (75 to 450 mg every 12 hours). Three patients were planned for treatment at each dose level; however, the exact number of patients treated at a specific dose level depended, as discussed below, on the number of patients within the cohort who experienced a DLT. If a patient in a given cohort experienced a DLT during Cycle 1, then subsequent patients were enrolled sequentially.

In all cohorts (including the first cohort), every patient was assessed for toxicity (based on CTCAE CCI [REDACTED] grading) on Days 15 and 29 of Cycle 1. Except for the initial cohort, patients in all subsequent cohorts were enrolled concurrently.

Table JPBA.6.1. Dose-Escalation Scheme for Study I3Y-MC-JPBA

| Cohort | Patients/Cohort | LY2835219 Dose |
|--------|-----------------|----------------|
| 1 | 3 | 50 mg Q24H |
| 2 | 3 | 100 mg Q24H |
| 3 | 3 | 150 mg Q24H |
| 4 | 3 | 225 mg Q24H |
| 5 | 3 | 75 mg Q12H |
| 6 | 3 | 100 mg Q12H |
| 7 | 3 | 150 mg Q12H |
| 8 | 3 | 200 mg Q12H |
| 9 | 3 | 275 mg Q12H |
| 10 | 3 | 350 mg Q12H |
| 11 | 3 | 450 mg Q12H |

Abbreviations: Q24H = every 24 hours, Q12H = every 12 hours.

Note: Cohorts 1-4 received study drug Q24H on the once daily schedule.

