9.1. General Considerations

Patients will be enrolled in this multicenter, open-label, Phase 1 study with dose escalation [REDACTED] design followed by dose confirmation in 6 tumor-specific expansions. During dose escalation, patients were enrolled [REDACTED] the total number of patients in a specific cohort was determined based on the occurrence of DLTs at that dose level (refer to Section 6.2.2), [REDACTED] During dose confirmation, at least 15 and up to 45-60 patients will be enrolled in each of 6 tumor-specific cohort expansions (refer to Section 6.2.3).

Statistical analysis of this study will be the responsibility of Eli Lilly and Company.

The analyses for this study will be descriptive. Data analyses will be provided [REDACTED] for all study patients combined wherever appropriate. For continuous variables, summary statistics will include number of patients, mean, median, standard deviation, standard error, minimum, and maximum. Categorical endpoints will be summarized using number of patients, frequency, percentages, and their standard errors. For time to event endpoints, the Kaplan-Meier curves (Kaplan and Meier 1958) will be estimated. Quartiles and rates at various time points, together with the 95% CIs, will be provided. Missing data will not be imputed.

The interpretation of the study results will be the responsibility of the investigator with the Lilly CRP, pharmacokineticist, statistician and Associate Consultant for Clinical Trial Management. The Lilly CRP and statistician will also be responsible for the appropriate conduct of an internal review process for both the final study report and any study-related material to be authorized for publication by Lilly.

[REDACTED]

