## 4. Study Objectives

### 4.1. Primary Objective

The primary objective of this study is to evaluate the safety and tolerability of LY2835219 when administered orally to patients with advanced cancer.

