### **6.3.9. Efficacy**

Efficacy assessments will be derived for patients during Dose Confirmation Phase (Parts B, C, D, E, F, and G).

Eastern Cooperative Oncology Group performance status (PS) will be listed and summarized for patients on therapy by cohort and cycle.

Reported lesion data (target or non-target) and investigator evaluation will be listed for patients on therapy.

Tumor markers will be listed for patients on therapy.

The best overall response, duration of overall response, duration of overall CR and duration of SD will be listed for patients on therapy. If appropriate, the efficacy endpoints, including Overall Response Rate, Disease Control Rate, Duration of Overall Response, Duration of

Overall CR, Duration of Stable Disease, PFS, and OS, will be summarized for Parts B, C, D, E F, and G.

The Overall Response Rate is defined as the proportion of patients who exhibits a confirmed CR or PR relative to baseline as defined by RECIST Version 1.1 (Eisenhauer et al. 2009). A responder is defined as any patient who exhibits a confirmed CR or PR relative to baseline assessment.

Disease Control Rate is defined as the proportion of patients in the analysis population who exhibit a SD or confirmed CR or PR relative to baseline during the study. Response is defined by RECIST Version 1.1 (Eisenhauer et al. 2009).

Overall Response Rate and Disease Control Rate with their respective 95% CI will be estimated using the Clopper-Pearson method. For time to event endpoints, including Duration of Overall Response, Duration of Overall CR, Duration of Stable Disease, PFS, and OS, the survival curve will be estimated by the Kaplan-Meier method (Kaplan and Meier 1958). Quartiles and rates at time points of every 3 months, together with the 95% CIs, will be provided.

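### For the safety rates, the only planned measure of precision by cohort is a standard error, which is zero at 0/n and n/n and understates upper uncertainty at low counts

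*SAP*

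**What the plan says.** The primary objective is to "evaluate the safety and tolerability of LY2835219 when administered orally to patients with advanced cancer" (SAP 4.1). The reporting rule for categorical endpoints is general. SAP 6.3.1 has them "summarized using number of patients, frequency, percentages, and their standard errors", and protocol 9.1 agrees: "Categorical endpoints will be summarized using number of patients, frequency, percentages, and their standard errors". The same SAP section adds: "The analyses for this study will be descriptive; no p-values will be calculated".

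SAP 6.3.5.1 (DLT and DLT-equivalent toxicities) and 6.3.5.2 (adverse events) call for summaries by cohort and name no interval for a cohort rate. SAP 6.3.5.1 does plan confidence limits, but they belong to the MTD estimated from a logistic model of DLT on dose.

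For two efficacy rates the SAP goes further: "Overall Response Rate and Disease Control Rate with their respective 95% CI will be estimated using the Clopper-Pearson method" (6.3.9).

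Part A cohorts are very small. Protocol 6.2.2 says "Three patients were planned for treatment at each dose level", and SAP 6.3.1 sets cohort size "based on the occurrence of DLTs (2-6 patients per cohort) at that dose level". Protocol 4.7 reports 2 DLTs in 3 patients at 275 mg Q12H, and "At the next lower dose level of 200 mg every 12 hours, 1 of the 7 patients also experienced DLT of Grade 3 fatigue". Expansion cohorts start at 15 patients and may reach 45 to 60.

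**The concern.** The standard error of a percentage is a large-sample summary. It fails where early safety data most often fall, at zero events or very few. A table entry of 0% with standard error 0 for a serious toxicity in 3 or 15 patients claims a certainty that the data cannot supply. At low non-zero counts, a reader who doubles the standard error gets an upper limit that is too low, and the upper side is the one that matters for toxicity. The study is also meant to support a recommended dose range for Phase 2. The SAP gives exact limits to rates that serve a secondary objective and withholds them from rates that serve the primary one.

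**Working it through.** **Inputs.** DLT counts 1/7 and 2/3 are from protocol 4.7. Planned cohort size 3 is from protocol 6.2.2. Expansion sizes 15 and 45 to 60 are from SAP 6.3.1. The diarrhea counts in 56 expansion patients are from protocol 4.7.

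**The plan's own figures.** Protocol 4.7 gives 30%, 16%, 5%, 0% and 0% for Grades 1 to 5. These reproduce: 17/56 = 30.4%, 9/56 = 16.1%, 3/56 = 5.4%, 0/56 = 0% twice. The documents print no standard error for any safety rate.

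**Formulas.**
- Standard error: SE = sqrt(p(1-p)/n) with p = x/n (assumed).
- Limits a reader would form from it: p ± 1.96 SE.
- Clopper-Pearson 95% limits: the 2.5% quantile of Beta(x, n-x+1) and the 97.5% quantile of Beta(x+1, n-x). For x = 0 the upper limit is 1 - 0.025^(1/n).

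**Numbers put in.**
- 0/3: SE = sqrt(0 × 1/3) = 0; exact upper limit 1 - 0.025^(1/3) = 70.8%.
- 1/7: SE = sqrt(0.143 × 0.857/7) = 13.2 points; 14.3% ± 25.9 gives -11.6% to 40.2%.

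| Count | Setting | Rate | SE (points) | ± 1.96 SE | Exact 95% |
|---|---|---|---|---|---|
| 0/3 | planned Part A size | 0% | 0 | 0% to 0% | 0% to 70.8% |
| 3/3 | planned Part A size | 100% | 0 | 100% to 100% | 29.2% to 100% |
| 1/3 | planned Part A size | 33.3% | 27.2 | -20.0% to 86.7% | 0.8% to 90.6% |
| 2/3 | DLT, 275 mg Q12H | 66.7% | 27.2 | 13.3% to 120.0% | 9.4% to 99.2% |
| 1/7 | DLT, 200 mg Q12H | 14.3% | 13.2 | -11.6% to 40.2% | 0.4% to 57.9% |
| 0/15 | smallest expansion | 0% | 0 | 0% to 0% | 0% to 21.8% |
| 1/15 | smallest expansion | 6.7% | 6.4 | -6.0% to 19.3% | 0.2% to 31.9% |
| 15/45 | larger expansion | 33.3% | 7.0 | 19.6% to 47.1% | 20.0% to 49.0% |
| 0/56 | Grade 4 diarrhea | 0% | 0 | 0% to 0% | 0% to 6.4% |
| 3/56 | Grade 3 diarrhea | 5.4% | 3.0 | -0.5% to 11.3% | 1.1% to 14.9% |

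**How often the SE is zero.** In a cohort of 3 the probability is (1-p)^3 + p^3. That is 73% at a true rate of 10%, 52% at 20% and 34% at 33%.

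**Coverage of p ± 1.96 SE at a true rate of 10%.** With n = 3, only the outcome 1/3 gives limits that contain 10%, so coverage is 3 × 0.1 × 0.9^2 = 24%. The same enumeration gives 52% for n = 7 and 79% for n = 15. Clopper-Pearson covers at least 98.7% in each case.

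**Where the SE is adequate.** For n = 45 and 60 at true rates of 10%, 20% and 33%, the mean estimated SE is 0.96 to 0.99 of the true SE, and coverage is 92% to 95%. At a true rate of 5% coverage falls to 90% (n = 45) and 81% (n = 60).

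**The case against.** Much of the case on the other side stands.

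- **No SE-based limits are planned.** The analysis is descriptive, and the limits and coverage figures above belong to an interval that a reader would have to build. That is true, and it is why one cannot say that the plan's error bars are wrong: it has none for safety rates. But the plan chose to report precision, and the zero at 0/n needs no interval to mislead. An exact interval is just as descriptive.
- **The SE is not always too small.** A reader might infer that it is far too small at all these cohort sizes. It is not. For 1/3 and 2/3 the SE-based interval is 1.19 times as wide as the exact one; the fault there is limits outside 0% to 100%. In expansions of 45 to 60 at common rates the SE is sound.
- **The 33% threshold does not separate the methods.** A reader might infer that the exact upper limit of 57.9% for 1/7 undermines the MTD. The SE-based limit of 40.2% also exceeds 33%, and so does the exact upper limit for 0/6, which is 45.9%. The MTD is defined on a proportion of patients and not on a confidence bound, so this reflects small cohorts and not the choice of summary.
- **No decision rests on the SE.** Escalation used DLT counts, and the expansion safety review is triggered by an observed proportion. Counts appear beside the percentage, DLTs and SAEs are listed individually, and the model-based MTD has its own confidence limits. This limits the consequence to reporting. The model's limits do not describe any cohort's rate.
- **Part of the plan is not visible.** SAP 6.3.1 contains a redaction, and the table shells are in a companion workbook (SAP 6.4). An interval for safety rates in either place would answer the point.

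**Conclusion.** The point holds as a fault in reported precision. Followed exactly, the stated rule prints zero uncertainty for any cohort with no events or all events, where the exact 95% upper limit for no events is 70.8% (n = 3), 21.8% (n = 15) or 6.4% (n = 56). It also understates the upper side at low counts, by about 18 points for 1/7 (57.9% against 40.2%) and about 13 points for 1/15 (31.9% against 19.3%). It does not show an error in the primary safety result, in the MTD rule or in any dose decision.

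The conclusion assumes the usual plug-in formula for the standard error, and that the redacted text and unseen table shells do not already specify intervals. The upper-side shortfalls also assume that a reader takes the standard error as plus or minus 1.96. The change is worth making because the better method is already in the SAP.

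**What to change.** In SAP 6.3.1 and protocol 9.1, make an exception to the general rule along these lines: *DLT, DLT-equivalent, Grade 3 or higher AE and SAE rates by cohort will be reported as count, denominator, percentage and exact (Clopper-Pearson) 95% confidence interval, in place of the standard error.* SAP 6.3.5.1 and 6.3.5.2 can then refer to that sentence. Other categorical summaries may stay as they are.

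The cost is a sentence in each document, a change of output statistic and slightly more output. No new data are needed. Stated precision will look less favourable, and Clopper-Pearson intervals are conservative in cohorts this small, with coverage of 98.7% or more in the cases checked at n = 3, 7 and 15 and a true rate of 10%.

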**Dose Escalation Phase (Part A)**

All data will be summarized by cohort (and all patients combined when appropriate), unless stated otherwise.

**Dose Confirmation Phase (Part B, C, D, E, F, and G)**

All data will be summarized by tumor-specific cohort:

- Part B: Non-small cell lung cancer of any subtype that is advanced and/or metastatic
- Part C: Glioblastoma multiforme (GBM) that has progressed or recurred after radiotherapy and/or chemotherapy
- Part D: Breast cancer that is advanced and/or metastatic
- Part E: Melanoma that is advanced and/or metastatic
- Part F: Colorectal cancer that is advanced and/or metastatic
- Part G: Breast cancer that is advanced and/or metastatic and hormone receptor positive.

The following data handling conventions ([Table JPBA 6.1](#)) will be used in the analysis:

**Table JPBA 6.1. Data Handling Conventions**

Term	Definition or Rule
Entered	Patients entered into the trial as those who sign the informed consent document directly or through their legally acceptable representatives.
Enrolled	Patients who are enrolled in the trial are those who have been assigned to a treatment.
On therapy	Patients who have received at least one dose of LY2835219.
Phase	This study has 2 phases: Dose Escalation Phase (Part A) and Dose Confirmation Phase (Part B, C, D, E F, and G).
Study day	
 
• There is no study day 0. Day -1 is the day before the day 1 of cycle 1 of each phase.
 
• Day -3 of cycle 1 of Dose Escalation Phase is the first dose of LY2835219.
 

Cycle day	
 
• There is no cycle day 0. Cycle day -1 is the day before the cycle day 1 of cycle 1 of each phase.
 
• Day -3 of cycle 1 is the first dose of LY2835219 in each phase. Day 1 of cycle 2 and beyond is the first dose of LY2835219 within cycle for each phase.
 

Treatment Day	Treatment Day relative to first day of the study (Cycle 1 Day -3).
Baseline	
For change from baseline analyses, baseline value is defined as the last reported measure on or before the first dose date (prior to the dose administration), unless otherwise specified.
 
For change from baseline within a cycle, baseline value is defined as the measure prior to the first dose of that cycle, unless otherwise specified.

The following are the General Reporting Requirements for the non-PK analyses (Table JPBA.6.2).

**Table JPBA.6.2. General Reporting Requirements for the Non-PK Analyses**

Variable	Requirements																		
Categorical variables	Report the formatted values																		
Statistical summary / Percentage	(if applicable) Round to the nearest tenths. For example, 45.6																		
Age	Round to the nearest tenths. For example, 49.3																		
Date	Report date in SAS date9 format (DDMMYY YYYY). For example, 11NOV2009																		
Laboratory results units	Report in SI units (International System of Units).																		
Laboratory values	
 
Report values up to a maximum of four significant digits.
 
No non-significant zeros for values less than four digits.
 
Use scientific notation to report values beyond the 1000th or 1/1000th.
 
 
Example:
 
  
 Actual Lab Values	Reported Lab Values	
   
 0.11123	0.1112	
 
 1.2034	1.203	
 
 1.2	1.2	
 
 10.234	10.23	
 
 102.345	102.3	
 
 1000.34	1000	
 
 12034	1.203E+4	
 
 0.000001	1.E-6	
  
	Actual Lab Values	Reported Lab Values	0.11123	0.1112	1.2034	1.203	1.2	1.2	10.234	10.23	102.345	102.3	1000.34	1000	12034	1.203E+4	0.000001	1.E-6
Actual Lab Values	Reported Lab Values																		
0.11123	0.1112																		
1.2034	1.203																		
1.2	1.2																		
10.234	10.23																		
102.345	102.3																		
1000.34	1000																		
12034	1.203E+4																		
0.000001	1.E-6																		

### **6.3.2. Patient Disposition**

All patients who discontinue from the treatment will be identified and the extent of their participation in the study will be reported. If known, a reason for their discontinuation will be given. This information will be listed and summarized for the end of Pre-study and end of study. All patients entered in the study will be accounted for in the summary of disposition by study phase. The number of patients who do not qualify for analysis, who die, or who discontinue before treatment begins will be specified. A patient will be considered to have received a cycle of treatment if they received any of the required treatments in that cycle. Follow-up disposition information will also be listed.

All clinically relevant protocol deviations will be listed by pre-determined categories (for example, inclusion/exclusion criteria, non-compliance with protocol procedures, drug dosage/intervention, use of excluded treatments, informed consent/assent process, continuing after meeting withdrawal criteria, or other).

Patient disposition will be summarized and listed for all enrolled patients.

### **6.3.3. Demographics and Baseline Characteristics**

#### **6.3.3.1. Demographics and Baseline Characteristics**

Patient demographic and baseline characteristics will be listed for all patients on therapy. At a minimum, patient demographics (sex, age, and race), baseline disease characteristics (Basis for diagnosis, initial pathological diagnosis, stage at initial diagnosis, baseline ECOG performance status, height, weight and derived body mass index [BMI]) will be listed and summarized by cohort/treatment group and overall by study phase.

In addition, alcohol and tobacco consumption habits will be listed for all patients on therapy.

